#### **4. Secondary Hypotheses and Sub-Analyses**

For the primary outcome, separate analyses will be conducted to evaluate each component of the composite. In addition, the rates of preterm birth <37 weeks will be evaluated. Specific aims 2 and 3 will also be investigated.

**4.1. Specific Aim 2:** To test the hypothesis that a lower diagnostic threshold for GDM at 14-18 weeks will result in improved detection of GDM and reduce the need for third-trimester testing.

##### **4.1.1. Secondary Hypothesis #1: Identification of a blood sugar value identified at early GDM screening that detects GDM outcomes and reduces the need for third-trimester screening**

*H0: There will be no association between early screening blood glucose levels and the rates of (a) hypoglycemic medication use, (b) the primary outcome, (c) macrosomia, and (d) third trimester testing in EGGO participants randomized to the Early screening group*

**4.1.2. Statistical Analysis:** Therefore, we will evaluate the ability of an early GDM screen to predict several outcomes. We will compare early GDM screening to GDM testing at 24-28 weeks with respect to the following outcomes: the need for hypoglycemic medications during pregnancy, the composite outcome from Specific Aim #1, macrosomia (a common complication of GDM), and third trimester testing. Logistic regression models will also be considered. Receiver operator characteristics (ROC) curves will be created to identify an ideal cut point. The area under the curve (the c statistic) will be used to assess the models.

**4.2. Specific Aim 3:** To test the hypothesis that 1,5-anhydroglucitol, a sensitive marker of recent hyperglycemic excursions, can be used as a simple and sensitive serum test for GDM in the obese population.

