 - iii. In those who are not diagnosed with GDM at the early screen, repeat testing will be performed at 24-28 weeks.
 - b. **Routine Screening Group.**
 - i. Women assigned to routine screening will have a blood draw for HbA1c and Glycomark between 14 weeks, 0 days and 20 weeks, 0 days gestation.

- If HbA1c $\geq 6.3\%$ in the routine screening group, the result will be unblinded and the clinician informed. These women will subsequently enter into routine GDM care with dietary counseling and patterned blood sugars.
 - If the patient is between 14 weeks, 0 days and 20 weeks, 0 days this blood draw may be performed at the enrollment visit. Otherwise, may be done in clinic with routine prenatal labs.
- ii. Women assigned to “routine screening” will undergo the 1-hour, 50-g glucose load (BSST) between 24 weeks, 0 days and 28 weeks, 0 days gestation. At the time of the BSST, a purple & gold top tube for HbA1c & Glycomark will be drawn (see baseline procedures below).

4. Results of Glucose screening tests

- a. Women whose BSST is ≥ 135 mg/dL, will be scheduled to undergo diagnostic testing with a 3-hour GTT (100-g glucose load). The currently used criteria to diagnose GDM (Carpenter Coustan criteria) will be used to diagnose GDM. By these criteria, a woman must have 2 elevated blood sugar values at either of the following timepoints and values:
1. Fasting ≥ 95 mg/dL
 2. 1-hour ≥ 180 mg/dL
 3. 2-hour ≥ 155 mg/dL
 4. 3-hour ≥ 140 mg/dL
- b. The attending physician will review the three-hour GTT results to confirm the diagnosis of GDM.
- c. Women who have a BSST > 200 will have a fasting blood sugar checked prior to undergoing a 3-hour GTT. If the fasting blood sugar < 126 mg/dL, the patient will proceed with a 3-hour GTT. If the fasting blood sugar ≥ 126 mg/dL, the diagnosis of GDM will be made.
- d. Women who are not diagnosed with GDM between 14-20 weeks (i.e. women who have a normal 1-hour BSST or who have an elevated 1-hour BSST but a normal 3-hour GTT) will repeat the 1-hour BSST at 24-28 weeks. At the time of the repeat BSST, a purple & red top tube for HbA1c & Glycomark will be drawn (see baseline procedures below).
- i. Women who are diagnosed with GDM will enter into routine GDM care with dietary counseling and patterned blood sugars. A purple & gold top tube for HbA1c & Glycomark will be drawn between 24-28 weeks, and 0 days gestation (see baseline procedures below).

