##### **4.2.1. Secondary Hypothesis #2: Association between AG levels and GDM diagnosis**

*H0: There will be no difference in the mean AG levels in EGGO participants with GDM and in EGGO participants without GDM.*

**4.2.2. Statistical Analysis:** The AG levels of women with and without GDM will be compared using a student's t-test or Mann-Whitney U test, as appropriate. A receiver operator characteristics curve will be created for AG to predict GDM (as diagnosed by a positive test at 24-28 weeks), need for hypoglycemic medications, and macrosomia. The area under the ROC curve will be calculated and an ideal cut-point for AG will be determined. The sensitivity, specificity, positive predictive value, and negative predictive value of AG will be determined.

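### Aim 2 is about detecting GDM, but SAP 4.1.1-4.1.2 lists no GDM outcome at 24-28 weeks, and the four listed outcomes depend partly on the early result

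*SAP*

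**What the plan says.** SAP 4.1 states Aim 2 as a test of whether "a lower diagnostic threshold for GDM at 14-18 weeks will result in improved detection of GDM and reduce the need for third-trimester testing". The null hypothesis in 4.1.1 concerns associations with early glucose "in EGGO participants randomized to the Early screening group", with no restriction to women left undiagnosed by the early screen. The outcomes in 4.1.2 are "the need for hypoglycemic medications during pregnancy, the composite outcome from Specific Aim #1, macrosomia (a common complication of GDM), and third trimester testing". The later test enters only as a comparator: "We will compare early GDM screening to GDM testing at 24-28 weeks with respect to the following outcomes". On the threshold, 4.1.2 says "Receiver operator characteristics (ROC) curves will be created to identify an ideal cut point", without naming the outcome the cut point is to be chosen on or the criterion for choosing it.

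Aim 3 is specified differently. SAP 4.2.2 will use AG to "predict GDM (as diagnosed by a positive test at 24-28 weeks), need for hypoglycemic medications, and macrosomia".

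The Protocol (Study Procedures) links the early result to what follows:
- Section 4.a: a BSST of 135 mg/dL or more leads to a 3-hour GTT. Section 4.c adds a fasting test for values above 200.
- Section 4.d: "Women who are diagnosed with GDM will enter into routine GDM care with dietary counseling and patterned blood sugars".
- Sections 3.a.iii and 4.d: in the Early arm, only women not diagnosed early repeat the BSST at 24-28 weeks.
- Section 3.b: the Routine arm has HbA1c and Glycomark drawn at 14-20 weeks, but no glucose load until 24-28 weeks.
- Section 8.d.v records medication as drugs prescribed for GDM. Section 8.c.ii records dates and values of BSST and GTT.

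**The concern.** A threshold study of detection needs a reference outcome that says who had the disease. Aim 2 has none, although the section that follows it uses one. What it has instead are outcomes that sit downstream of the early test. If an early glucose value helps decide who is diagnosed, treated and retested, a ROC curve against those consequences describes the trial's own pathway as well as the disease.

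The women who matter most for a lower threshold are those below 135 mg/dL at the early screen. They have no GTT at that time, so no early diagnosis exists against which a lower BSST cut-off could be checked. Only their 24-28 week retest can show who among them went on to be diagnosed. A cut point chosen without that outcome could be reported as a detection threshold when it has not been tested as one.

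**Working it through.** **1. The plan's own figure.** SAP 3.1.3 is the only sample-size basis, and it sizes the primary outcome. With 50% against 25%, two-sided alpha 0.05 and 80% power:

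n = [1.960 × √(2 × 0.375 × 0.625) + 0.842 × √(0.25 + 0.1875)]² / 0.25² = (1.342 + 0.557)² / 0.0625 ≈ 57.7, so 58 with GDM per group.

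58 / 0.10 = 580 per arm. Both figures reproduce. Aim 2 has no size or precision statement of its own.

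**2. Each listed outcome against the Protocol.** I read the early value as the BSST, the glucose test planned for every Early-arm woman.

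| Outcome | Link to the early result |
|---|---|
| Medication | Follows a GDM diagnosis, which the early BSST helps produce. Women below 135 early can still be diagnosed and medicated after the retest. |
| Macrosomia, composite | Women diagnosed early receive GDM care from then on, which the trial expects to lower risk. |
| Third-trimester testing | Fixed by protocol: not diagnosed early means retested. |

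**3. Size of the distortion (all inputs assumed).** One simulation of 500,000 women used 10% GDM, 25-75% of it found early, log-odds slopes of 0.3 or 0.6 per SD of early glucose, base risks of 50% or 20%, risk halved in women diagnosed early, and 40% of diagnosed women medicated. The halving borrows the size of the planned difference in SAP 3.1.3, which is a between-group difference in a combined endpoint and not an estimate of treatment effect on macrosomia.

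- Macrosomia or composite: AUC falls by 0.009 (0.582 to 0.573) to 0.041 (0.656 to 0.615).
- Not being retested: AUC 0.93-0.95, because the early diagnosis decides it.

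A second simulation (14% macrosomia) gave AUC falls of 0.599 − 0.586 = 0.013 to 0.606 − 0.579 = 0.027. With 580 × 0.14 ≈ 81 events, the Hanley-McNeil standard error is about 0.035, so that shift is below one standard error.

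For medication, two further sets of assumed correlations gave whole-arm AUCs of 0.82-0.88 and 0.84-0.89. The matching values if every woman were retested untreated were 0.81-0.83 and 0.84-0.86. Most of that AUC is real prediction, although the cut point drifts toward the screening cut-off as more GDM is found early.

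**4. What the added outcome can support.** Take 580 women, 10% GDM (58 cases) and an assumed share s found early. Late cases = 58(1 − s); analysis set = 580 − 58s. For an assumed AUC A = 0.70, with n₁ late cases and n₂ others:

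SE² = [A(1 − A) + (n₁ − 1)(a − A²) + (n₂ − 1)(b − A²)] / (n₁n₂), with a = A/(2 − A) = 0.5385 and b = 2A²/(1 + A) = 0.5765.

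At s = 50%, n₁ = 29 and n₂ = 551 − 29 = 522: SE² = (0.21 + 1.36 + 45.05) / 15,138 = 0.00308, and 1.96 × SE = 0.109. For an assumed sensitivity of 70%: 1.96 × √(0.21/29) = 0.167.

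| s | Late cases | Analysis set | AUC ± | Sensitivity ± |
|---|---|---|---|---|
| 25% | 43.5 | 565.5 | 0.089 | 13.6 points |
| 50% | 29 | 551 | 0.109 | 16.7 points |
| 75% | 14.5 | 536.5 | 0.153 | 23.6 points |

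Over the 6-20% GDM range in SAP 3.1.3, late cases run from 580 × 0.06 × 0.25 ≈ 9 to 580 × 0.20 × 0.75 = 87.

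**5. The price of restricting the set.** Leaving out women diagnosed early removes true positives with high BSST and keeps GTT-negative women above 135. Under the same two sets of assumed correlations:

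| | Restricted set | Untreated retest of everyone |
|---|---|---|
| AUC, first set | 0.77-0.79 | 0.82-0.84 |
| AUC, second set | 0.80-0.82 | 0.84-0.86 |
| Youden cut point, first set | 57th-61st percentile | 67th-69th |
| Youden cut point, second set | 61st-63rd percentile | 69th-71st |

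Restriction lowers the AUC and pulls the cut point down.

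**The case against.** The strongest defence is that the choice of outcomes is deliberate. The heading of 4.1.1 speaks of GDM outcomes, and a threshold may reasonably be judged by clinical consequences. That justifies keeping medication, macrosomia and the composite. It does not supply the detection half of the aim.

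The 24-28 week test is named as comparator. This does not fill the gap: women diagnosed early have no repeat BSST, Routine women have no BSST at 14-20 weeks, and no GDM endpoint is defined from the comparison. Third-trimester testing might be meant as the test result, but the null hypothesis speaks of its rate and the aim of the need for it, so the SAP would have to say so. SAP section 5 allows laboratory and GDM comparisons, but only as concepts subject to committee approval.

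Two objections stand. First, the effect of treatment on the macrosomia and composite curves is modest. A reader might infer that early glucose defines the medication outcome; the retest pathway contradicts that, since women below 135 early can be diagnosed later. Second, a set limited to women not diagnosed early is selected on the predictor, and its effect on the cut point is not small. That set should therefore be added with its limits stated, and should not be the sole basis for a threshold.

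**Conclusion.** The point holds as a gap in specification. Aim 2 asks about detection, and 4.1.1-4.1.2 contain no outcome that measures it. The listed outcomes are partly driven by the early result, and one of them is fixed by it. Following the plan exactly, the whole-arm ROC would not by itself show what a lower early threshold detects.

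The missing outcome rests on the text alone and needs no simulation. The simulated distortion of the other outcomes depends on assumed correlations, treatment effect and share found early, and should be read for direction only.

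A reader might go further and infer that the trial cannot answer Aim 2. The documents do not support that: women not diagnosed early are not given GDM care at that stage, are due for retest, and have dated BSST and GTT values recorded. The answer would be imprecise, but it can be obtained. This is a secondary aim, so the change should be made before the Aim 2 analysis; nothing in the primary analysis depends on it.

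**What to change.** In SAP 4.1.1-4.1.2:

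1. Add, as the detection outcome, GDM diagnosed at the planned 24-28 week retest among Early-arm women not diagnosed at 14-20 weeks. For candidate BSST thresholds below 135 mg/dL, report sensitivity, specificity and added yield (late cases whose early value lay between the candidate and 135), each with a confidence interval.
2. Report medication use, macrosomia and the composite separately for women diagnosed early and not diagnosed early. Do not base the cut point on them alone.
3. Replace outcome (d) with the result of the 24-28 week test.
4. Name the outcome and criterion by which the cut point is chosen.
5. State the limits: few late cases; a set that omits women diagnosed early and so lowers the AUC and shifts a ROC-optimal cut point downward; and late cases that may be new disease and not missed disease.

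The cost is SAP wording and one added analysis on data already collected. The price in precision is the wide intervals shown in the working.

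### SAP 4.1.2 never compares its ROC cut point with the 135 mg/dL in use, so a cut below 135 is not in itself evidence for a lower early threshold

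*SAP*

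**What the plan says.** SAP 4.1 states Aim 2 with a direction: "a lower diagnostic threshold for GDM at 14-18 weeks will result in improved detection of GDM", and with less need for third-trimester testing. The formal null in SAP 4.1.1 has no direction and covers the whole glucose range: "There will be no association between early screening blood glucose levels and the rates of" four outcomes.

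SAP 4.1.2 lists those outcomes as "the need for hypoglycemic medications during pregnancy, the composite outcome from Specific Aim #1, macrosomia (a common complication of GDM), and third trimester testing". It plans a comparison of early screening with testing at 24–28 weeks, possible logistic models, and this: "Receiver operator characteristics (ROC) curves will be created to identify an ideal cut point". It adds: "The area under the curve (the c statistic) will be used to assess the models".

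The value in use appears only in the protocol, item 4.a: "Women whose BSST is ≥ 135 mg/dL, will be scheduled to undergo diagnostic testing with a 3-hour GTT (100-g glucose load". Diagnosis then rests on the GTT criteria. Item 3.a.iii sets the retest rule: "In those who are not diagnosed with GDM at the early screen, repeat testing will be performed at 24-28 weeks".

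The SAP does not name the ROC criterion or give an interval for the cut. It does not make the cut conditional on the AUC or the association test, and it does not mention 135. Neither document gives a distribution of early screening glucose or a screen-positive rate.

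**The concern.** The aim is about a lower threshold, but none of the planned outputs tests one. Rejecting the null of no association is compatible with all the excess risk lying at or above 135, which would be an argument for leaving the threshold alone. The AUC summarises discrimination over all cuts and says nothing about any particular one. Only the position of the ROC cut could be read as lower, and the usual criteria give sensitivity and specificity equal weight. That draws the cut towards the middle of the glucose distribution. If 135 lies in the upper part of that distribution, a cut below it is a likely result whether or not a lower threshold has merit.

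At stake is a secondary conclusion. The trial could report support for a lower early threshold, and so for labelling more women, without having shown that performance at the lower value is better than at 135.

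**Working it through.** **Inputs.** The Early group is 580 women (SAP 3.1.3). The current screening value is 135 mg/dL (Protocol 4.a). The share q of women at or above 135 is not given; 15–40% is assumed. The ROC criterion is not given either, so the Youden index (maximum of sensitivity + specificity − 1) and the closest-to-corner rule (minimum of (1 − sensitivity)² + (1 − specificity)²) were both used.

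**The plan's own figure.** For 50% vs 25%, two-sided 0.05, 80% power:

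n = [1.960·√(2·0.375·0.625) + 0.842·√(0.5·0.5 + 0.25·0.75)]² / 0.25² = (1.342 + 0.557)² / 0.0625 ≈ 57.7, so 58 per group, and 58/0.10 = 580.

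This reproduces. It sizes the primary comparison; no power or error rate is stated for the Aim 2 cut.

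**Step 1: no association.** The estimated ROC curve wanders randomly about the diagonal, and the Youden maximum is about equally likely at any glucose quantile. Hence P(cut < 135) ≈ 1 − q. On the diagonal the corner distance is (1 − t)² + t², which is smallest at t = 0.5, so that rule settles near the median. Simulation with n = 580 agrees:

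| Screen positive (q) | 15% | 20% | 30% | 40% |
|---|---|---|---|---|
| 1 − q | 85% | 80% | 70% | 60% |
| Youden cut below 135 | 85% | 80% | 70% | 60% |

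The closest-to-corner cut was below 135 in about 84–100% over the same range.

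A second set of runs used assumed normal glucose in mg/dL. Means of 100–130 with SD 20–30 gave 54–92% (Youden) and 65–100% (corner). At mean 135 the figures were 49–51% and 33–40%; at mean 140, 40–44% and 7–13%. The result therefore depends on median glucose being below 135.

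**Step 2: risk flat below 135 and higher only from 135 upwards.** Here the risk pattern gives no reason for a lower threshold. Clearly below means more than 0.1 SD below 135. Risks were 8% vs 16%, 35% vs 50% and 40% vs 45%.

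| Screen positive | Youden cut clearly below 135 | Corner cut clearly below 135 |
|---|---|---|
| 15–20% | 52–77% | 97–100% |
| 30% | 37–59% | 65–99% |

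**Step 3: would a significance gate help?** Under no association it largely would: only about 2–3% of samples had both a significant association and a cut below 135. Under the 35% vs 50% step at 20–30% screen positive, a significant association and a cut clearly below 135 still occurred together in about 32–36% (Youden) or 55–74% (corner).

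**Step 4: steeper steps.** With 2% vs 20% or 3% vs 30%, the Youden cut was clearly below 135 in about 7–10% of samples at 20% screen positive, 2–4% at 30% and 0–1% at 40%. The corner cut was clearly below in 0–1% at 30%, but in up to 54% at 15%.

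**Step 5: third-trimester testing.** Under the protocol only women at or above 135 who are then diagnosed avoid the retest. Simulated that way, the cut fell below 135 in 0% of samples.

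**The case against.** Three objections carry weight.

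First, the SAP nowhere says that a cut below 135 would count as support for Aim 2. It also plans an AUC, an association test and a comparison with testing at 24–28 weeks, so a worthless predictor would usually show itself. This stands, and a reader should not infer that the SAP decides Aim 2 by the cut's position. What remains is that the plan offers no other comparison that bears on lower, and Step 3 shows that a significant association does not rule out a misleading cut.

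Second, it is tempting to say that the method gives a cut below 135 for any outcome, almost regardless of the data. The documents do not support that. Third-trimester testing is fixed by the early result, so a no-association case cannot arise if the protocol is followed. Medication use is tied to 135 because a result at or above it opens the path to diagnosis and treatment. Steep steps mostly place the cut near 135 once 20% or more screen positive.

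Third, the glucose distribution and the ROC criterion are assumptions, and the Youden figures under no association simply restate the assumed q. That is correct, which is why ranges are given. If median early glucose were 135 or higher, the tendency would disappear or reverse.

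In addition, Aim 2 speaks of a diagnostic threshold, whereas 135 is a screening value. SAP 4.1.1 points to early screening glucose, but the SAP does not settle which is meant.

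**Conclusion.** The concern holds in a limited form. For the composite and macrosomia, and less clearly for medication use, an ROC cut below 135 is not evidence that a lower threshold is warranted, because SAP 4.1.2 has no step that sets the cut against 135. It does not hold for third-trimester testing.

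The frequencies in the working rest on fewer than half of women screening positive, on 580 women with usable data, and on one of the two common ROC criteria. The absence of a comparison with 135 depends on none of these.

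Severity is minor. Aim 2 is secondary and without stated power, and the primary analysis is untouched. The correction is nearly free and would prevent an unsupported statement about the threshold.

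**What to change.** In SAP 4.1.2:

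- State that the position of the ROC cut point does not by itself support Aim 2.
- Name the ROC criterion, and say whether the threshold in question is the screening value or the diagnostic GTT criteria.
- Report the cut with a bootstrap 95% confidence interval, and the bootstrap difference in sensitivity and in specificity between the cut and 135. Reselect the cut in each bootstrap sample.
- For medication use, the composite and macrosomia only, add a logistic regression on continuous early glucose in Early-group women below 135, to show whether risk rises below the current value. Treat it as supportive and not as the sole deciding test: a rising risk does not show that any particular lower cut performs better. It cannot be fitted for third-trimester testing, because by protocol every woman below 135 is retested.

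The cost is SAP wording and a little extra analysis of data already collected. The regression has low power. With a 40% outcome and an odds ratio of 1.35 per SD, it is 64% at 20% screen positive and 51% at 30%. With a 5% outcome and a log odds ratio of 0.7 per SD, it is 49% and 33%. A null result there would not show that risk is flat below 135.

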##### **4.2.1. Secondary Hypothesis #2: Association between AG levels and GDM diagnosis**

*H0: There will be no difference in the mean AG levels in EGGO participants with GDM and in EGGO participants without GDM.*

**4.2.2. Statistical Analysis:** The AG levels of women with and without GDM will be compared using a student's t-test or Mann-Whitney U test, as appropriate. A receiver operator characteristics curve will be created for AG to predict GDM (as diagnosed by a positive test at 24-28 weeks), need for hypoglycemic medications, and macrosomia. The area under the ROC curve will be calculated and an ideal cut-point for AG will be determined. The sensitivity, specificity, positive predictive value, and negative predictive value of AG will be determined.

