- ii. Women who are not diagnosed with GDM (i.e. women who have a normal 1-hour BSST or who have an elevated 1-hour BSST but a normal 3-hour GTT) will continue routine prenatal care.
- iii. Women who are diagnosed with GDM will enter into routine GDM care with dietary counseling and patterned blood sugars.

5. Baseline Procedures

- Measurement of height, without shoes, at time of enrollment.
- Record self-reported prepregnancy weight.
- All women will have a blood draw for HbA1c and Glycomark between 14 weeks, 0 days and 20 weeks, 0 days gestation. The blood for HbA1c should be collected in a purple top tube (3mL). The blood for Glycomark should be collected in a gold top tube (3mL).
 - Women undergoing early GDM screening may have these blood samples drawn at the time of the blood draw for the 1-hour BSST.
 - Women randomized to routine screening may have these blood samples drawn at the time of randomization if between 14 weeks, 0 days and 20 week, 0 days. Otherwise, they may have the blood drawn at their clinic at an appropriate time (i.e. at the time of other routine prenatal lab draws).
 - Samples will be labeled with patient name plate for transport to OBGYN lab.
 - Samples may be stored at room temperature or 4°C (refrigerated) for up to 7 days.
- All women will have a blood draw for HbA1c and Glycomark between 24 weeks, 0 days and 28 weeks, 0 days gestation. The blood for HbA1c should be collected in a purple top tube (3mL). The blood for Glycomark should be collected in a gold top tube (3mL).
 - This blood draw may be performed at the time of the 1-hour BSST.
 - Women diagnosed with GDM prior to 24-28 weeks may have the blood drawn in clinic at the appropriate gestational age, in conjunction with routine prenatal lab draws or separately.
 - Samples will be labeled with patient name plate for transport to OBGYN lab.
 - Samples may be stored at room temperature or 4°C (refrigerated) for up to 7 days.
- Trained and experienced research staff in obstetric and perinatal outcomes abstraction will be responsible for all research data abstraction from patient medical records.
- Maternal outcomes will be ascertained in the hospital following delivery and at the routinely scheduled follow-up visit at 4-6 weeks after delivery.
- Newborn outcomes will be ascertained until 6 weeks after delivery through maternal questioning regarding re-admission. Readmissions for infants will be validated through medical review.

6. Follow-up

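### Aim 3: the AG ROC curve defines GDM by a 24-28 week test that the protocol does not plan for Early-arm women already diagnosed at 14-20 weeks

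*SAP*

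**What the plan says.** **SAP, Aim 3.** Section 4.2 asks whether AG "can be used as a simple and sensitive serum test for GDM in the obese population" and sets no time limit on the diagnosis. The null hypothesis in 4.2.1 compares mean AG "in EGGO participants with GDM and in EGGO participants without GDM", again without a time limit or a split by arm. Section 4.2.2 then has two analyses:

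- a comparison of means or ranks: "The AG levels of women with and without GDM will be compared using a student's t-test or Mann-Whitney U test";
- an ROC curve, "created for AG to predict GDM (as diagnosed by a positive test at 24-28 weeks". Need for hypoglycemic medication and macrosomia are the other two ROC outcomes. Sensitivity, specificity, PPV, NPV and a cut-point are to be reported.

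The section does not say which AG sample enters the curve.

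**Protocol, testing.** Item 3.a.iii, for the Early group: "In those who are not diagnosed with GDM at the early screen, repeat testing will be performed at 24-28 weeks". Item 4.d repeats this, covering women with a normal BSST and those "who have an elevated 1-hour BSST but a normal 3-hour GTT) will repeat the 1-hour BSST at 24-28 weeks". For women with GDM, item 4.d.i gives GDM care and then: "A purple & gold top tube for HbA1c & Glycomark will be drawn between 24-28 weeks". It names no glucose test for them at that visit.

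**Protocol, samples.** Section 5: "All women will have a blood draw for HbA1c and Glycomark between 14 weeks, 0 days and 20 weeks, 0 days gestation". It plans a second draw for all women at 24-28 weeks. I take the Glycomark draw to be the AG measurement.

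**SAP, Aim 2.** Sections 4.1.1 and 4.1.2 list third-trimester testing among four outcomes to be related to early glucose in the Early arm. The term is not defined.

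**The concern.** The ROC definition depends on a test that a known group of cases is not scheduled to have. An Early-arm woman diagnosed at 14-20 weeks has GDM for Aim 3 as stated and for the t-test, but cannot meet the ROC definition. A Routine-arm woman is ordinarily first tested at 24-28 weeks, so the definition captures her. One section therefore carries two meanings of GDM, and the ROC meaning works differently by arm.

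What is at stake is the interpretation of the reported accuracy, mainly PPV and the cut-point. They would describe GDM diagnosed later, while the aim concerns GDM in obese women generally. If the handling is left open, it may be settled after results are known.

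A related, lesser question arises in Aim 2. If third-trimester testing means the 24-28 week retest, the protocol itself assigns it from the early result.

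**Working it through.** **Inputs from SAP 3.1.3.** Adverse-outcome rates of 50% and 25%, alpha 0.05 (two-sided per 3.1.2), 80% power, GDM incidence 10% (reported range 6-20%).

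**The plan's figure.** With pooled variance and no continuity correction:

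n = [1.960·√(2·0.375·0.625) + 0.842·√(0.25 + 0.1875)]² / 0.25² = 57.7, so 58 GDM cases per group.

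58/0.10 = 580 women per group and 1,160 in total. This reproduces the SAP. Pooled, that is 116 cases and 1,160 − 116 = 1,044 non-cases.

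**Assumptions not in the documents.** Share f of Early-arm GDM found at 14-20 weeks: 25%, 50% or 75%. Equal total GDM incidence in both arms. Sensitivity and specificity of AG both 0.80.

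**Cases without the reference test.** e = 58f = 14.5, 29 or 43.5, which is 12.5%, 25% or 37.5% of 116. The cases left number 101.5, 87 or 72.5.

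**PPV at 10% incidence.** False positives = 0.2 × 1,044 = 208.8.

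- Either test: 92.8/(92.8 + 208.8) = 0.308
- Early cases excluded: 0.8(116 − e)/[0.8(116 − e) + 208.8]
- Early cases scored as non-cases: 0.8(116 − e)/301.6

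| f | e | PPV, either test | PPV, excluded | PPV, non-cases |
|---|---|---|---|---|
| 25% | 14.5 | 0.308 | 0.280 | 0.269 |
| 50% | 29 | 0.308 | 0.250 | 0.231 |
| 75% | 43.5 | 0.308 | 0.217 | 0.192 |

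Over the SAP's incidence range, with 1,160 women: at 6% (69.6 cases), 0.203 for either test against 0.183, 0.161 and 0.138 with exclusion; at 20% (232 cases), 0.500 against 0.467, 0.429 and 0.385.

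**NPV at 10%.** Either test: 835.2/(835.2 + 23.2) = 0.973. With exclusion or non-case scoring it is 0.976, 0.980 or 0.983.

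**AUC, if early and late cases have similar AG.** Take 0.80. Exclusion leaves it unchanged. Non-case scoring gives (1,044 × 0.8 + e × 0.5)/(1,044 + e) = 0.796, 0.792 or 0.788. The Hanley-McNeil standard error is 0.025 with 116 cases and 0.027, 0.029 or 0.032 with the cases left after exclusion.

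**AUC, if early cases deviate more.** Assume a binormal model with shifts of 1.2 SD for early-diagnosed and 0.8 SD for all other GDM. Exclusion gives 0.714, against 0.725, 0.736 or 0.747 for GDM at either test. The gap of 0.011-0.033 is 0.4-1.2 standard errors and reflects case mix.

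**Aim 2, on the retest reading and with full adherence.** Every woman with BSST below 135 mg/dL is retested. At or above 135, retesting depends on the GTT, or on the fasting value when BSST exceeds 200. Let s be the share with BSST at or above 135 (assumed 15-40%) and d the share diagnosed early (incidence × f). If BSST carries no further information above 135, the rule alone gives

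AUC = [(1 − s) + 0.5(s − d)]/(1 − d).

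At 10% incidence this runs from (0.60 + 0.1875)/0.975 = 0.81 (s = 0.40, d = 0.025) to (0.85 + 0.0375)/0.925 = 0.96 (s = 0.15, d = 0.075). Over 6-20% incidence it runs from about 0.80 to 1.0. With the full early work-up as predictor it is 1.0 by construction.

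**The case against.** The timed definition may be deliberate. The SAP's verb is predict, 24-28 weeks is the one testing window planned in both arms, and leaving known cases out of a prediction of later diagnosis is an ordinary design. On that view a label would suffice. The harm also looks small: AUC and NPV hardly move, and the lower PPV under exclusion is mostly the lower prevalence of a narrower target. The t-test and the medication and macrosomia curves do not need the 24-28 week test. The PPV figures rest on assumed inputs.

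Most of this stands as a limit on size. It does not remove the mismatch, because the aim sets no time limit and the SAP neither says that a narrower target is meant nor says what happens to early cases.

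A reader might infer that the SAP drops these women. It does not say so. Exclusion and non-case scoring are what the literal definition leaves. The authors may have meant an earlier diagnosis to count as a case, but the text does not say that either.

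A reader might also infer that the Aim 2 curve is certainly circular. The documents do not go that far. The heading of 4.1.1 and the wording of Aim 2 favour the retest reading without settling it, and 4.1.2 does not list which outcomes get an ROC curve.

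An either-test definition has its own weakness: Early women have two chances of diagnosis and Routine women one.

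**Conclusion.** The point holds as a mismatch between the SAP's ROC case definition and the protocol's testing schedule. Between 12.5% and 37.5% of planned GDM cases cannot be counted as cases under the literal definition, if 25-75% of Early-arm GDM is found early. The visible effect is on PPV: 0.31 falls to 0.22-0.28 with exclusion or 0.19-0.27 with non-case scoring, at 10% incidence and sensitivity and specificity of 0.80. None of the three assumed inputs is in the documents.

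It would be too strong to say that the ROC analysis as a whole is badly biased. AUC and NPV change by about 0.01 or less when early and late cases have similar AG. A larger AUC gap needs early cases to differ in AG, which the documents do not establish.

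The Aim 2 point is subordinate and conditional on the retest reading. Both concern secondary aims; the primary analysis is unaffected. The change is worth making because it needs no new data.

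**What to change.** **Aim 3, main curve.** Count GDM diagnosed at either protocol test as a case and use the 14-20 week AG sample, which is planned for all women. Report results by arm as well as pooled, because of the unequal chances of diagnosis.

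**Aim 3, 24-28 week AG curve.** If kept, restrict it to women not already in GDM care and label it later-diagnosed GDM.

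**Routine women with HbA1c ≥6.3%.** Protocol 3.b.i sends them into GDM care before the routine screen and does not say whether they still have it. State how they are classified, for example with a sensitivity analysis without them.

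**Aim 2.** Define third-trimester testing. If it is the 24-28 week retest, do not choose an ROC cut-point on it. Tabulate instead, for each candidate early threshold, retests avoided, later GDM cases captured and false positives.

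**Cost.** SAP wording and minor programming, on data already planned. By-arm estimates are less precise: with 58 cases per arm the AUC standard error is about 0.036, against 0.025 pooled. The restricted 24-28 week curve has no fewer Early-arm cases than the current definition already yields.
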